Men with progressive metastatic CRPC received 2 fractionated doses two weeks apart. Initially, 6 cohorts of 3-6 pts got 2 doses of ^{177}Lu -J591 2 weeks apart (20 mCi/m², escalating to 45 mCi/m² x2). Subsequently, pts enrolled in 2 expansion cohorts at the recommended phase 2 doses (RP2D). Planar ^{177}Lu -J591 imaging was semi-quantitatively scored. The endpoints were PSA changes and survival (OS); as well as CTC count (CellSearch) changes in the expansion cohorts. 49 patients, with median age 74.1 years (range 55-95), median PSA of 44.9 ng/mL (1.9-766.5); 83.7% with bone, 61.2% with lymph node, 40.8% with visceral metastasis. 8.2% were CALGB (Halabi) low, 34.7% were intermediate, 57.1% were in high-risk group. RP2D's of fractionated ^{177}Lu -J591 were 40 mCi/m² x2 or 45 mCi/m² x2 with option for GCSF. PSA changes for the low dose group were reported as 6.3% showing >50% PSA decline, 12.5% reporting >30% PSA decline, and 37.5% with any PSA decline. within RP2D group 21.2% showing >50% PSA decline, 42.4% reporting >30% PSA decline, and 66.7% with any PSA decline. The median overall survival for low dose group was 14.6 months and for RP2D group was 27.7 months. Accurate targeting of ^{177}Lu -J591 was seen in 79.6%. Patients with lower PSMA expression by imaging were less likely to respond ($p=0.07$). Of 25 with CTC counts, 14 declined, 8 stably favorable, and 3 increased. RP2D was associated with more PSA declines ($p=0.036$) and longer OS ($p=0.004$), even after controlling for CALGB prognostic grouping (adjusted HR 0.42 [95% CI 0.21, 0.84] $p=0.01$). Predictable, reversible myelosuppression was seen. 36 (73.5%) patients had grade 3/4 heme toxicities; 19 (57.6%) had Grade 4 heme toxicities in RP2D cohorts with 45.4% receiving prophylactic platelet transfusions (median 1, range 1-4) and 6 GCSF. 14 (28.6%) had infusion reactions (without pre-meds), with 1 patient having Grade 2 infusion reaction leading to withdrawing from the study prior to his 2nd dose. 5 (10.2%) had transient Gr 1/2 AST/ALT. This study concluded that fractionated ^{177}Lu -J591 is well tolerated with predictable, reversible myelosuppression and PSA and CTC declines. Additionally, with dose-fractionation, the cumulative dose MTD is 14-28% higher than single dose MTD with similar toxicity.

Table 5: Toxicities data from Phase 2 single dose ^{177}Lu -J591 Study and Phase 1 fractionated ^{177}Lu -J591 study:

Cumulative Dose (mCi/m ²)	Single Dose		Fractionated Dose		

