10.1 CTC count response

All subjects in this study will get blood samples drawn (at screening and EOS visit) for CTC enumeration by CellSearch methodology. Our primary analysis will assess those whose CTC counts drop to less than 5 or stay below 5 (responders) vs. those who remain at least 5 or above (non-responders) at EOS visit.

In addition, it appears that decreases in CTC counts with therapy are a favorable marker even if the count remains at least 5. We will also analyze % changes in CTC counts with at least 50% decline in CTC count from baseline considered a response at 12 weeks. Best response will also analyzed (% increase or best % decrease at any point will also be reported in a waterfall plot).

As reported in phase III studies of men with mCRPC, a favorable CTC count and LDH level at 12 weeks has been associated with overall survival. We will report the

proportion of subjects who have CTC count <5 and normal LDH at the initial scan (efficacy) visit time point.

Additional reports associate an undetectable CTC count at 12 weeks as prognostic. We will report the proportion of subjects who have an undetectable CTC count at the initial scan (efficacy) visit time point.

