10.2 Biochemical (PSA) response

PSA response will be determined by comparing the PSA levels after therapy to the baseline, pre-treatment PSA. Declines of $\geq 30\%$ confirmed by a second PSA value ≥ 2 weeks later, will be reported. Subjects must not demonstrate clinical or radiographic (CT and/or MR) evidence of disease progression during this time period.

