10.4 Duration of CTC response

Duration of CTC response is defined from the first CTC count drop to <5 (or $\leq 50\%$ of baseline) to the time CTC count increases to ≥ 5 (or $\geq 25\%$ increase from nadir).

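### The supplementary CTC response rule (a fall of 50% or more) has no minimum baseline count, so at 1-2 cells sampling noise alone often meets it, and at 0 cells it is undefined

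*Combined protocol and SAP*

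**What the plan says.** Section 10.1 draws CTC samples from everyone: "All subjects in this study will get blood samples drawn (at screening and EOS visit) for CTC enumeration by CellSearch methodology". The main CTC analysis there classifies patients by whether the count falls or stays below 5. A second analysis is then introduced because "decreases in CTC counts with therapy are a favorable marker even if the count remains at least 5", and its rule is "at least 50% decline in CTC count from baseline considered a response at 12 weeks". A waterfall plot of percent change is also planned.

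The section states no minimum baseline, no handling of a baseline of 0 and no confirming draw. Nothing elsewhere supplies them:
- Section 3.2 (eligibility) sets no CTC minimum.
- Section 10.4 starts the duration of CTC response at a count below 5 or at no more than half of baseline, again without a floor.
- Analysis of Efficacy (under 10.8) promises a CTC response proportion with a 95% interval but does not say which definition it uses.
- Section 12.5.2 plans only description.

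**The concern.** The stated reason can apply only to patients who start at 5 or more, since a count that falls and is still at least 5 must have started above 5. The rule as written is wider. It also scores 1 cell to 0, or 2 cells to 1, as a response, and whole-number counts that low differ between two draws by sampling alone.

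The protocol is more careful with PSA. Response in 10.2 must be "confirmed by a second PSA value", and the percent rises in 10.3, 10.5 and 10.7 also need an absolute change of 2 ng/mL. The CTC rule has neither safeguard, and Table 8 schedules only one post-treatment enumeration, at the scan visit.

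Low counts are to be expected. Section 2.5 reports for the earlier fractionated J591 study: "Of 25 with CTC counts, 14 declined, 8 stably favorable, and 3 increased". Two things are at stake: a CTC decline rate partly made of noise, and a denominator that two analysts could define differently because patients at 0 cannot be classified.

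**Working it through.** The documents give no error rate for this rule, so there is no plan figure to reproduce. Everything below assumes that both counts are Poisson with the same true mean, that is, no treatment effect.

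**Inputs from the documents.** A fall of at least 50% at week 12 (10.1); cut-off of 5 cells per 7.5 mL (2.7.2 and 10.1); 8 of 25 = 32% stably favorable in the J591 study (2.5).

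**1. Given the observed baseline b.** The rule is met when the second count is at most floor(b/2). With the true mean set equal to b:
- b = 1: P(0) = e^-1 = 0.368
- b = 2: P(0 or 1) = 3e^-2 = 0.406
- b = 5: P(at most 2) = 0.125
- b = 6: P(at most 3) = 0.151
- b = 10: P(at most 5) = 0.067
- b = 20: P(at most 10) = 0.011

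**2. Range when the true mean is uncertain given b.** Poisson-gamma predictive probabilities at b = 1 and b = 2:
- flat prior: 0.25 and 0.31
- Jeffreys prior: 0.35 and 0.40
- 1/mean prior: 0.50 and 0.50

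With a common fixed mean and baselines 1 and 2 pooled, the result is 0.27 at mean 2, 0.49 at mean 1, and 0.57-0.67 at means of 0.75-0.5.

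**3. Baseline 0.** The percent change divides by zero. Such patients occur with probability e^-1 = 0.37 at true mean 1 and e^-2 = 0.14 at true mean 2.

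**4. Effect on the reported rate.** The joint probability of a baseline of at least 1 and a fall of at least 50% is the sum over x ≥ 1 of P(X1 = x) × P(X2 ≤ floor(x/2)). This gives 0.333 at mean 1 and 0.320 at mean 2. Dividing by P(X1 ≥ 1), which is 0.632 and 0.865, gives 0.53 and 0.37. If 32% of patients are low-count:
- zeros kept as non-responders: 0.32 × 0.333 = 0.107 and 0.32 × 0.320 = 0.102, about 10-11 points
- all with a detectable baseline: 0.32 × 0.53 = 0.17 and 0.32 × 0.37 = 0.12, so 12-17 points

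**5. After a floor of 5.** The no-effect rate is 12.5% at baseline 5, 15% at 6, 6.7% at 10 and 1.1% at 20. Patients whose true mean is 3-5 but who start at 5 or more by chance still regress: 0.54 at mean 3 and 0.27 at mean 5.

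**The case against.** The strongest reply is that the intent is readable. The rule follows directly on a sentence about counts that stay at 5 or above, so the gap is a missing phrase and not a decision to score 1 to 0 as drug effect. That is fair as to intent, but the written rule is what a programmer will apply, and it has no limit.

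Second, low-count patients are covered elsewhere in 10.1. Those who stay below 5 are responders in the main analysis, and two further analyses report a count below 5 with normal LDH, and an undetectable count. This stands. A reader might infer that patients at 0 drop out of the CTC results; they are unclassifiable only under the percent rule.

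Third, nothing is decided on this rule. The MTD rests on DLTs, the Simon decision on PSA, and CTC response is descriptive. This also stands. A reader might infer that the headline CTC proportion is inflated, but 10.1 names the below-5 analysis as primary, and the documents do not show that the percent rule feeds the reported proportion.

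Fourth, the J591 figure is weak support. It comes from a different agent, its baseline distribution is not given, and favorable counts include 0. Its summary also lists stably favorable patients separately from those who declined. So 12-17 points is an upper case, not the expected size.

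Finally, noise produces rises as well as falls, so the waterfall plot is made noisy at low counts, not simply biased downward.

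**Conclusion.** The point holds as a minor gap in definition. The rule reaches further than its own reason, and at observed baselines of 1-2 cells about 37-41% of unchanged patients would meet it, with a plausible range of 25-50%. It would be tempting to say that noise alone produces a response half the time. One half is the upper end of that range, it applies only at 1-2 cells, and it is not a strict ceiling, since a true mean below 1 gives more. Nor do low-count patients carry no information; they carry little under this particular measure.

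The effect on the supplementary rate is about 10-11 points with zeros as non-responders, up to 12-17 if every low-count patient has a detectable baseline. Both figures rest on the Poisson model, a true mean of 1-2, and a low-count share of about a third, none of which the documents establish for this trial. Assay variability beyond Poisson would add noise.

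**What to change.** In 10.1, state that a fall of at least 50% at week 12 is analysed as a response, and shown in the percent-change waterfall plot, only for subjects with a baseline CTC count of at least 5 per 7.5 mL. For baselines of 0-4, list the baseline and week-12 counts without a percent change. Put the same limit on the half-of-baseline start of CTC response duration in 10.4. The cut-off is the protocol's own and matches the reason it gives.

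The change is wording only. The price is a smaller denominator: if 32% are excluded, 68% remain, and at the same proportion the interval widens by about √(1/0.68) = 1.21, or some 21%. Low-count patients stay in the below-5, CTC/LDH and undetectable-count analyses. Because the floor lessens but does not remove noise and regression to the mean just above 5, the report should show the individual counts beside the rate.

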10.2 Biochemical (PSA) response

PSA response will be determined by comparing the PSA levels after therapy to the baseline, pre-treatment PSA. Declines of $\geq 30\%$ confirmed by a second PSA value ≥ 2 weeks later, will be reported. Subjects must not demonstrate clinical or radiographic (CT and/or MR) evidence of disease progression during this time period.

10.3 Duration of PSA response

Duration of PSA response is defined as the time from the first 25% PSA decline until the PSA value is confirmed to increase by 25% above the nadir, provided that the increase is at least 2 ng/mL above the nadir.

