10.6 PSA Stabilization

PSA stabilization is referred to as any set of PSA values that do not meet the criteria for PSA response or PSA progression.

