12.2. Phase II

We will enroll up to 27 subjects into the Phase II portion (including the 3-6 used for establishing the MTD). We will define evaluable patients as patients who met eligibility requirements, have initiated therapy, and were not removed from the study for non-compliance or patient withdrawal.

Sample size recommendations for the two-stage design are determined according to Simon's two-stage minimax design. We project a 30% PSA decline proportion of 35%, below which the regimen will be unacceptable and a 30% PSA decline proportion of 60%, above which the regimen will be considered worthy of further exploration. The null hypothesis that the 30% PSA decline proportion is less than or equal to 35% will be tested against the alternative hypothesis that the 30% PSA decline proportion is greater than or equal to 60%.

The sample size computations were performed assuming a 0.10 one-sided level of significance and 90% power assuming a historical control value for PSA decline of 35% and the alternative hypothesis of 60%. If 6 or fewer of the first 16 evaluable patients do not experience a 30% decline in PSA (stage 1), the study will be terminated and declared to have a negative result. If 7 or more patients out of the first 16 evaluable patients experience a 30% decline in PSA, ongoing accrual will proceed to the target sample size of 27 patients (stage 2). The new regimen will be declared active in this patient population and worthy of further testing if 13 or more patients experience a 30% PSA decline among the 27 patients entered. This two-stage design yields a 0.90 probability of a positive result if the true 30% PSA decline proportion is 60%. It yields a 0.90 probability of a negative result if the true 30% PSA decline proportion is 35%. An exact 95% binomial confidence interval will be constructed for the proportion of patients with PSA decline.

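### Section 10.3 starts duration of PSA response at an unconfirmed 25% decline, while Section 10.2 requires a confirmed 30% decline for response

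*Combined protocol and SAP*

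**What the plan says.** Section 10.3 gives the start of the clock as follows: "Duration of PSA response is defined as the time from the first 25% PSA decline until". The clock stops when "the PSA value is confirmed to increase by 25% above the nadir, provided that the increase is at least 2 ng/mL above the nadir". The rise must be confirmed, but no confirmation is asked of the decline, and the measure is not limited to patients who meet the response criterion.

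Section 10.2, headed as biochemical (PSA) response, uses declines of at least 30% from the pre-treatment value, "confirmed by a second PSA value" at least 2 weeks later. It adds a further condition: "Subjects must not demonstrate clinical or radiographic (CT and/or MR) evidence of disease progression during this time period".

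Section 10.6 covers everyone else: "PSA stabilization is referred to as any set of PSA values that do not meet the criteria for PSA response or PSA progression".

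The phase II test also works at 30%. Section 12.2 states: "The null hypothesis that the 30% PSA decline proportion is less than or equal to 35% will be tested against the alternative" (an alternative of 60% or more). Section 4.2 uses the same 30% decline.

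**The concern.** A duration of response should describe the patients who responded and should run from the moment they did. Section 10.3 secures neither. Its threshold is five percentage points below the one in 10.2, it drops the confirmation, and it omits the condition of no clinical or radiographic progression. A 25% decline is not a response criterion anywhere else in the plan, and no section reconciles the two figures.

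Two consequences follow from the wording:

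- A patient whose best decline lies between 25% and 30% is not a responder under 10.2 and is stable under 10.6 until he progresses, yet he has a duration of response under 10.3.
- A responder who passes through that band at an earlier visit has time counted before his response.

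What is at stake is the coherence of a descriptive result: the patients with a duration would not be the patients counted as responders under 10.2.

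**Working it through.** The plan states no figure for duration of response, so there is none to reproduce. The check compares the definitions and then runs invented PSA series through them.

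**Definitions compared**

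| | Threshold | Decline confirmed? | Limited to responders? |
|---|---|---|---|
| PSA response (10.2) | at least 30% | yes, at least 2 weeks later | not applicable |
| Start of PSA duration (10.3) | 25% | not stated | not stated |
| CTC response (10.1) | below 5, or at least 50% decline | – | not applicable |
| Start of CTC duration (10.4) | below 5, or at most 50% of baseline | – | – |

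For CTC, the duration clock starts at the plan's own response thresholds. For PSA it does not.

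**Visit schedule.** From Table 8 and Section 6.1.4, PSA is drawn on nominal Days 1, 15, 29, 57 and 85, then every 4 weeks (Days 113, 141, 169). The intervals after Day 1 are 14, 14, 28 and 28 days, then 28.

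**Assumptions.** Declines are measured from Day 1. The end is dated at the first PSA that is at least 1.25 × nadir and at least 2 ng/mL above it, confirmed at the next visit.

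**Time added for a responder with the same end date under both starts** = (day 30% first reached) − (day 25% first reached).

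- Both thresholds crossed at the same visit: 0 days.
- Down 27% on Day 29 and 35% on Day 57: 57 − 29 = 28 days.
- In the band on Day 15, past 30% on Day 29: 29 − 15 = 14 days.

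**Series A, never reaches 30%.** PSA 100, 90, 74, 73, 73, 80, 95, 110 on Days 1, 15, 29, 57, 85, 113, 141, 169.
- Best decline: (100 − 73)/100 = 27%.
- Start at 25%: Day 29 (74, down 26%).
- End: 1.25 × 73 = 91.25, first met on Day 141 (95; rise 22 ng/mL), confirmed by 110.
- Duration under 10.3: 141 − 29 = 112 days. With a 30% start: none.

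**Series B, a responder.** PSA 100, 74, 72, 60, 50, 55, 70, 80 on the same days.
- Start at 25%: Day 15 (down 26%). Start at 30%: Day 57 (down 40%), confirmed on Day 85 (down 50%).
- End: 1.25 × 50 = 62.5, first met on Day 141 (70; rise 20 ng/mL), confirmed by 80.
- Duration: 141 − 15 = 126 days against 141 − 57 = 84 days, a difference of 42 days. He is in the band at two visits, so the excess spans two intervals.

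**Series C, a short-lived decline that never reaches 30%.** PSA 100, 90, 73, 92, 95 on Days 1, 15, 29, 57, 85.
- End: 92 exceeds 91.25 on Day 57 (rise 19 ng/mL), confirmed by 95.
- Duration under 10.3: 57 − 29 = 28 days. With a 30% start: none.

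**Direction for a group.** With a 30% start limited to responders, only B contributes, and the median is 84 days in either pairing below.
- A and B under 10.3: (112 + 126)/2 = 119 days, higher.
- C and B under 10.3: (28 + 126)/2 = 77 days, lower.

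**Phase II test, for context.** With 16 patients in stage 1 (continue at 7 or more) and 27 in total (active at 13 or more), the probability of a positive result at true proportion p is the sum over x = 7 to 16 of P(X₁ = x) × P(X₂ ≥ 13 − x), with X₁ ~ Bin(16, p) and X₂ ~ Bin(11, p). This gives 0.0979 at p = 0.35 and 0.9001 at p = 0.60, in line with the stated 0.10 and 90%. Nothing in 10.3 enters this calculation.

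**The case against.** The strongest reply is that the title of 10.3 and its place directly after 10.2 imply a restriction to responders. A sensible analyst would apply it, and series A and C would then drop out. That is a fair reading, but the restriction is not written, and even with it the early start in series B remains.

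One can also say that 10.2 only promises to report declines of 30% rather than defining response. Its heading, the reference in 10.6 to criteria for PSA response, and the phase II endpoint nonetheless leave 30% as the only response threshold in the plan.

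On size, the objection largely stands. The extra time arises only if a scheduled PSA falls in a five-point band before a later one reaches 30%. The documents give no data on how often that happens, and the series above are illustrations, not trial data.

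A reader might infer more than the text supports:

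- *That reported durations will be overstated as a whole.* This is not established. For a single responder with the same end date the 25% start can only lengthen the duration or leave it unchanged, but added non-responders may have short durations and pull a median down.
- *That the measure will be shown beside the phase II result.* Nothing says so. It is not among the objectives (Protocol Summary; Sections 1.1 to 1.3), the endpoints listed in the Protocol Summary, or the measures named under Analysis of Efficacy in Section 10.8. Section 12.5.2 promises only descriptive analysis of PSA response.
- *That the end point of 10.3 is also at fault.* It already requires a confirmed rise with an absolute minimum. For a responder, whose nadir is below baseline, it is nearly the progression rule in 10.5.

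**Conclusion.** The concern holds as an internal inconsistency with a limited effect. Section 10.3 uses an unconfirmed 25% decline where 10.2 uses a confirmed 30% decline. As written, it can assign a duration of response to a non-responder and can count time before response in a responder. For a responder the excess is typically one visit interval, 14 or 28 days on the nominal schedule. It can be more (42 days in the worked example) and is zero when both thresholds are crossed at once.

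How often this would occur and which way a group median would move cannot be determined from the documents. The finding rests on reading 25% as a decline from baseline and on taking 10.3 literally. It does not bear on the phase II test, sample size, type I error or power.

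**What to change.** Reword Section 10.3 along these lines: in patients with a PSA response per Section 10.2, duration of PSA response is the time from the first PSA showing the decline of at least 30% that is later confirmed, until the end point already given in 10.3 (confirmed 25% rise above nadir, at least 2 ng/mL). If the 25% start is deliberate, the section should say why and name the measure differently.

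The cost is one sentence, with no new visits, samples or patients. Individual responders' durations may be slightly shorter, and patients who never meet 10.2 will have none.

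This aligns duration with the responders of 10.2. It does not by itself guarantee a match to the phase II count, because Sections 4.2 and 12.2 refer to a 30% decline without restating the confirmation and no-progression conditions. The report should therefore state which set of responders the durations describe.

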10.4 Duration of CTC response

Duration of CTC response is defined from the first CTC count drop to <5 (or $\leq 50\%$ of baseline) to the time CTC count increases to ≥ 5 (or $\geq 25\%$ increase from nadir).

10.5 PSA Progression

PSA progression will be defined as a rise of $> 25\%$ above either the pretreatment level or the nadir PSA level (whichever is lowest). PSA must increase by > 2 ng/ml to be considered progression. Confirmation requires a second consecutive rising PSA at least 2 weeks apart.

